7.5 SECONDARY ENDPOINT(S)

7.5.1 Key secondary endpoint(s)

This section is not applicable as no key secondary endpoint has been specified in the protocol.

7.5.2 Secondary endpoint(s)

No MCPMod dose finding analyses or subgroup analyses will be performed for secondary endpoints.

Responder secondary endpoints

The analysis of responder secondary endpoints will be performed on the FAS, using planned maintenance treatment, and including all data censored for COVID-19 related early treatment discontinuation.

A frequency table will be presented of those patients achieving percentage change from baseline in body weight at each time point (up to and including Week 46) of $\leq -5\%$, $\leq -10\%$, $\leq -15\%$ and $\leq -20\%$, respectively.

The analysis of responder secondary endpoints (which are defined only at Week 46) will be aligned with the estimand strategy specified in [Section 7.4.1](#) for the primary analysis. This will be done using a multiple imputation approach on the underlying continuous body weight values, as specified below. Missing body weight measurements will be imputed using actual values of body weight, not changes from baseline. The same random seed will be used as specified for the multiple imputation sensitivity analysis of the primary endpoint in [Section 7.4.2](#).

As the first step, non-monotone (intermediate) missing values will be imputed using the MCMC method. The details of the MCMC imputation step are exactly the same as those given in [Section 7.4.2](#).

Next, the remaining monotone missing values at each week will be imputed using the sequential regression method on each of the 1000 partially imputed datasets above. The imputations will be performed using the MAR assumption, which assumes that a patient with a missing value follows a similar trajectory to a similar patient without missing data in the same treatment group (where “similar patient” means with regard to both baseline covariates and non-missing values). The order in which the imputation model is specified is important for this step, and will be as follows: treatment, gender, baseline body weight, body weight at each scheduled post-baseline week in numeric week order.

Percentage change in body weight from baseline will then be derived for each patient in each of the 1000 completely imputed datasets, and from this each of the 3 responder definitions will also be derived for each patient. In other words, the multiple imputation steps will only be performed once for all relevant responder endpoints.

Each of the 1000 completely imputed datasets will be analysed using logistic regression with treatment group and gender as factors and baseline body weight as a continuous linear covariate. The model will be used to estimate the log (odds ratio) and its 95% CI for each of the BI 456906 doses compared with placebo.

The overall blinded proportion of responders using each of the 3 responder definitions will be reviewed at the RPMs. If necessary following this review, a decision may be made to adapt the standard logistic regression model to use a method to handle the possible situation of zero events in any treatment group (if so, then penalised regression using Firth's bias reduction method will be used).

The estimates of log(odds ratio) and their 95% CIs will be pooled across the 1000 imputed datasets using Rubin's rules (which appropriately allow for the within and between imputation variance), and then transformed to the odds ratio scale for display in a suitable summary table. The estimated proportion of responders in each treatment group will also be displayed.

[REDACTED]

[REDACTED]

[REDACTED]

Continuous secondary endpoints

The analysis of continuous secondary endpoints will be performed on the FAS, using planned maintenance treatment, and including only on-treatment data, regardless of whether early treatment discontinuation was COVID-19 related.

It should be particularly noted here that off-treatment data capture after early treatment discontinuation which relates to endpoints other than those derived from body weight is not expected in any structured way according to the protocol, even if some data may still nevertheless exist.

[figure not shown]
For blood pressure endpoints, only pre-dose measurements or measurements captured at a visit where no dosing was performed will be used, as described in [Section 6.7](#).

[figure not shown]
Descriptive statistics will be presented over time for each of the continuous secondary endpoint variables (absolute changes from baseline in body weight, waist circumference, systolic BP and diastolic BP). All scheduled weeks will be presented, although the secondary endpoints themselves are only defined at Week 46.

An MMRM will be fitted in turn to each continuous secondary endpoint variable at each scheduled week. The MMRM will include the same model terms as for the primary analysis described in [Section 7.4.1](#), except that, where necessary, baseline body weight will be replaced by the baseline corresponding to the relevant endpoint. Unstructured covariance will be assumed to model the relationship between pairs of measurements taken at different weeks on the same patient. If the model fails to converge, similar attempts to address this will be made as for the primary analysis.

A summary table will be produced for each continuous secondary endpoint of the MMRM results at each time point, including adjusted means (using the observed margins approach) and their standard errors for each treatment group, and adjusted mean differences from placebo for each BI 456906 dose group and their 95% CIs.

Adjusted means from the MMRM for each continuous secondary endpoint will also be displayed graphically over time to assess the onset of effect over time.

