7.4 RANDOMISATION

BI will arrange for the randomisation and the packaging and labelling of trial medication. The randomisation list(s) will be generated using a validated system, which involves a pseudo-random number generator so that the resulting treatment will be both reproducible and non-predictable. The block size will be documented in the Clinical Trial Report (CTR). Access to the codes will be controlled and documented.

Patients will be randomised in blocks using equal allocations to one of 5 double-blind treatment groups. Randomisation will be performed at the start of the dose escalation period at Day 1, Visit 2 (starting dose and timing of dose escalation as outlined in [Table 4.1.4: 1](#)), with allocation to one of the following target maintenance period treatments:

- Placebo once weekly
- BI 456906 0.6 mg once weekly
- BI 456906 2.4 mg once weekly
- BI 456906 3.6 mg once weekly
- BI 456906 4.8 mg once weekly

Randomisation will be stratified by gender. It is anticipated that no more than 70% women will be randomised.

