7.5 DETERMINATION OF SAMPLE SIZE

Sample size evaluation was performed using simulation in R software (version 3.6.1), with 10000 simulations performed for each scenario summarised below.

The sample size calculation was based on the following assumptions:

- An overall significance level of 2.5% (one-sided) for the contrast test of the null hypothesis of flat dose response
- The (monotone) dose response shapes specified in [Section 7.2.2](#)
- A placebo effect size (mean percentage change from baseline in body weight at Week 46) of zero
- A maximum effect size (mean percentage change from baseline in body weight at Week 46) in the highest dose group of -10.0%
- A standard deviation of 7.0% [[R20-0479](#)].

Simulations were also performed to investigate departures from the assumed true maximum effect stated above, as well as for different scenarios for the true nature of the dose response relationship. The probability of success for each of these scenarios is summarised in [Table 7.5: 1](#) below.

A success was defined as meeting all 3 of the following criteria:

1. Null hypothesis of flat dose response was rejected in favour of at least one of the alternative candidate models, and
2. A target dose was selected within the dose range using the following criterion: difference in mean between selected dose and placebo < -9.0%, and
3. Proportion of patients in the highest dose group meeting the responder definition (percentage change in body weight from baseline < -10.0%) was greater than 35%.

Table 7.5: 1 Probability of success with N=70 patients in each treatment group and SD = 7.0%.

| | Probability of success (%) | | | | | | |
|-------------------------|----------------------------|-------------|-------------|--------------------|--------------------|---------------------|-------------|
| | | Linear | Exponential | E _{max} 1 | E _{max} 2 | SigE _{max} | AVERAGE |
| True maximum effect (%) | -9.0 | 48.9 | 48.9 | 48.8 | 49.0 | 65.3 | 52.2 |
| | -9.5 | 67.8 | 68.3 | 69.1 | 67.9 | 79.2 | 70.5 |
| | -10.0 | 82.8 | 83.3 | 83.8 | 83.3 | 89.0 | 84.4 |
| | -10.5 | 92.4 | 92.6 | 93.2 | 92.2 | 95.6 | 93.2 |
| | -11.0 | 97.1 | 97.3 | 97.8 | 96.5 | 98.4 | 97.4 |

A sample size of 70 patients per treatment group gives a probability of success of greater than 80% for all assumed dose response shapes, with the assumed maximum dose effect and standard deviation as stated earlier.

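### The blinded all-arm responder proportion that decides the switch to Firth regression says almost nothing about an empty placebo arm, so the ≥15% odds ratios may not be estimable

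*SAP*

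**What the plan says.** SAP 7.5.2 derives the three responder endpoints (loss of at least 5, 10 and 15% at Week 46) from 1000 imputed datasets. Each dataset is analysed by logistic regression on treatment, gender and baseline weight. The log odds ratios of each dose against placebo are pooled by Rubin's rules.

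The section foresees that an arm might have no responders. The safeguard has two steps. First, "The overall blinded proportion of responders using each of the 3 responder definitions will be reviewed at the RPMs". Then, if thought necessary, "a decision may be made to adapt the standard logistic regression model to use a method to handle the possible situation of zero events". This applies to whichever arm is empty, and the method named for that case is Firth's penalised regression.

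No numerical cut-off is attached to the review. The visible text has no check of arm-level counts after unblinding, and no rule for the case where an arm is empty in some imputed datasets but not in others. Redacted blocks follow the pooling paragraph, so this describes the visible text only. Protocol 7.2.3 gives the same logistic model with no provision for empty arms.

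**The concern.** Zero events is a property of one arm, but the reviewed quantity is pooled over all five. The higher doses supply most of the ≥15% responders, so the pooled figure can look comfortable while placebo has none.

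Placebo is the comparator for every odds ratio. If it is empty, the maximum-likelihood log odds ratios for all four doses diverge together. If only an active arm is empty, that arm's odds ratio diverges. With multiple imputation the condition can differ between datasets, and Rubin's rules would then average diverged fits with finite ones. The alternative is to change the model after the arm counts are known, which a SAP signed before database lock (SAP 3) is meant to avoid.

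**Working it through.** **Inputs** (Protocol 7.4 and 7.5)
- Five equal arms: "Patients will be randomised in blocks using equal allocations to one of 5 double-blind treatment groups", with 70 patients each.
- Placebo: "A placebo effect size (mean percentage change from baseline in body weight at Week 46) of zero".
- Top dose: "A maximum effect size (mean percentage change from baseline in body weight at Week 46) in the highest dose group of -10.0" per cent.
- Spread: "A standard deviation of 7.0" per cent.
- The five candidate shapes of Protocol 7.2.2.

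**The plan's own figures first.** A simulation of the success criteria in Protocol 7.5 (10,000 runs per scenario, one-sided 2.5%, critical value 2.23) gave 82.7, 83.1, 83.9, 82.4 and 89.7% at a true effect of -10. Table 7.5:1 has 82.8, 83.3, 83.8, 83.3 and 89.0%. The average is 84.4% in both. The contrasts match SAP Table 7.4.1:1 to three decimals, so the shapes below are those of the plan.

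**Step 1: an empty placebo arm.** Assuming normality, p = Φ((-15 - mean)/SD) = Φ(-15/7) = 1.61%.
- Expected responders: 70 × 0.0161 = 1.12 (1.1 after rounding).
- P(none) = (1 - 0.0161)^70 = 32.2%.
- At ≥10%: p = Φ(-10/7) = 7.66% and P(none) = 0.4%. At ≥5% it is about 6 × 10⁻⁹. The problem is confined to the 15% threshold.

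**Step 2: any empty arm, and the pooled proportion.** For arm j, p_j uses that arm's mean under the shape. P(any arm empty) = 1 - Π[1 - (1 - p_j)^70]; the values shown come from 300,000 simulated trials per shape. All entries are percentages.

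| Shape | p_j: placebo, 0.6, 2.4, 3.6, 4.8 mg | P(any arm empty) | Mean overall proportion | Same, placebo empty |
|---|---|---|---|---|
| Linear | 1.6, 2.5, 7.7, 14.2, 23.8 | 44 | 9.94 | 9.63 |
| Exponential | 1.6, 1.8, 3.5, 7.7, 23.8 | 55 | 7.66 | 7.33 |
| Emax 1 | 1.6, 9.6, 19.9, 22.4, 23.8 | 32 | 15.46 | 15.14 |
| Emax 2 | 1.6, 4.6, 14.8, 19.9, 23.8 | 35 | 12.95 | 12.63 |
| Sigmoid Emax | 1.6, 1.7, 8.9, 18.4, 23.8 | 53 | 10.87 | 10.55 |

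The small shift is simple arithmetic: emptying placebo removes 1.12 expected responders, and 1.12/350 = 0.32 percentage points. Comparing trials with placebo empty and not empty, the gap is about 0.5 points (linear: 9.63 against 10.09). The 5th-95th percentile ranges nearly coincide (linear: 7.1-12.3 against 7.7-12.6). From the lowest to the highest quartile of the overall proportion, P(placebo empty) falls only from about 40% to 25%.

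**Step 3: sensitivity** (these means and SDs are assumptions, not plan values). P(no placebo responder) with SD 7: 20.0% at mean -1, 10.5% at -2, 4.5% at -3, 1.5% at -4. With mean 0: 65% at SD 6 and 11.5% at SD 8.

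**Step 4: does imputation repair it?** The documents give no dropout rate, so the number missing is assumed. If no observed placebo patient responds and m are missing, an imputed dataset keeps an empty placebo arm with probability of roughly (1 - 0.0161)^m: 92% for m = 5, 85% for m = 10, 72% for m = 20. Most fits would diverge and some would not.

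**Step 5: the two estimators.** In a simulated dataset with 0/70 on placebo and 15/70 at 4.8 mg, maximum likelihood gave a log odds ratio of 7.9 (SE 7.2) after 8 iterations and 24.9 (SE about 35,000) after 25. These values show divergence and depend on where iteration stops; they are not effect sizes. Firth gave an odds ratio of 38 (95% CI 2.3 to 636). With 3/70 against 20/70, maximum likelihood gave about 9.2 and Firth 7.9 (2.4 to 26).

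**The case against.** A reader might infer that the plan has no fallback. It has one: the SAP names Firth's method, and because the review has no cut-off, the team may adopt it as a precaution on any blinded result. A team that knows placebo is a fifth of the patients could well do so. What stands is narrower: nothing visible makes that happen, and the figure under review cannot guide the choice. Because of the redactions, a further rule cannot be ruled out.

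A reader might also infer that the pooled proportion carries no information at all. It carries a little, as the fall from 40% to 25% shows, but far too little to decide on.

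The 32% rests on a placebo mean of zero, a sample-size simplification. SAP 7.4.1 notes that the contrast test does not use it. Every arm receives diet and activity counselling (Protocol 3.1), and Protocol 4.1.2 expects at 0.6 mg a modest weight reduction similar to placebo, which implies some loss on placebo. This objection stands: the risk may be a few per cent rather than a third. It does not make the trigger more informative.

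Finally, the stakes are limited. The protocol plans no confirmatory testing, there are no key secondary endpoints, and the frequency tables by arm are reported anyway. A late switch would be to a method already named, and Firth's interval with an empty placebo arm is very wide. All of this is fair and bears on priority.

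**Conclusion.** The concern holds in a limited form. The condition that the safeguard is meant to catch is nearly invisible in the quantity that triggers it. On the plan's assumptions (normality, placebo mean 0, SD 7, 70 analysed per arm), the ≥15% endpoint has a 32% chance of an empty placebo arm and a 32-55% chance of at least one empty arm, while the expected overall proportion moves by about 0.3 points. If placebo patients lose 2 to 4% on average, the placebo risk is 10.5 to 1.5%.

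Unless the Report Planning Meeting adopts Firth as a precaution, all four ≥15% odds ratios may diverge or need a change of method after unblinding. It would be wrong to conclude that dose finding is at risk: the MMRM and MCPMod analysis uses the continuous endpoint and is untouched. The ≥5% and ≥10% endpoints are practically safe. The change is worth making because it is cheap, not because the trial's main conclusion depends on it.

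**What to change.** For the ≥15% endpoint, name Firth penalised logistic regression as the planned model in every imputed dataset, and drop the blinded-proportion review for it. Using it for all three responder endpoints would be simplest and keeps them on one model.

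If a trigger is preferred, make it automatic after unblinding: for any endpoint where any arm has 0% or 100% responders in any imputed dataset, use Firth in all imputed datasets for that endpoint. This prevents mixing two estimators under Rubin's rules and leaves nothing to judgement.

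The cost is a sentence in SAP 7.5.2 and a software option. The sample size does not change. When no arm is empty, the odds ratios shrink slightly towards 1, as in the example above (7.9 against about 9.2).

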5.2.2 Secondary endpoint(s)

Secondary endpoints are defined as follows:

- Weight loss of $\geq 5\%$ from baseline at Week 46 (yes/no)
- Weight loss of $\geq 10\%$ from baseline at Week 46 (yes/no)
- Weight loss of $\geq 15\%$ from baseline at Week 46 (yes/no)
- Absolute change from baseline in body weight, measured in units of kg, at Week 46.

[figure not shown]
All secondary endpoints defined using body weight will use clinic visit measurements of body weight, similarly to the primary endpoint.

[figure not shown]
- Absolute change from baseline in waist circumference, measured in units of cm, at Week 46.
- Absolute change from baseline in systolic blood pressure, measured in units of mmHg, at Week 46.
- Absolute change from baseline in diastolic blood pressure, measured in units of mmHg, at Week 46.

For the blood pressure endpoints, there is an additional time point structure within each scheduled week. Three measurements are planned to be captured at each of these time points within week. The mean of these three measurements (or the mean of the available measurements if fewer) will be calculated and used in the endpoint definitions. Further details are given in [Section 6.7](#).

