6.1.6 Definition of On-Treatment

It is particularly noted here that the protocol encourages continued study participation for patients who have discontinued treatment early. It is therefore expected that for some patients there will be off-treatment data captured during the planned treatment period.

In addition, even for patients who completed treatment according to the protocol, data captured during the follow-up period may be relevant for safety.

With these points in mind, it is important to be clear whether all available data will be used in a particular summary or analysis, or whether only on-treatment data will be used. The definition of “on-treatment” for this purpose is as described below. It is assumed that all patients will have

a date of last administration of study medication accurately recorded on the End of Treatment eCRF page.

“Off-treatment” refers to data which are captured after baseline but which are not “on-treatment” as defined below.

Safety

An AE start date or other safety assessment date will be considered “on-treatment” if the AE start date or assessment date is between the date of first dose and 28 days after the date of last dose of study treatment inclusive (the residual effect period (REP) is defined as 28 days in this trial).

The same on-treatment definition will be used for all types of safety data.

Efficacy

Efficacy data will also use the same 28 day definition of “on-treatment” as for safety.

The same on-treatment definition will be used for all types of efficacy data, including for all exploratory biomarkers (irrespective of whether the latter are specified as further endpoints or not).

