Prior to applying the visit windows specified below, it will first be determined whether the data record is on-treatment, as defined in [Section 6.1.6](#), for summaries or analysis which require this approach.

Unscheduled and repeat assessments (where relevant/available) are eligible for inclusion in visit windows.

For all variables except 12-lead ECG, if a patient has more than one non-missing value within the same visit window, the value closest to the target day will be selected. If two non-missing values are the same distance from the target day, the earlier of the two values will be selected.

For 12-lead ECG (only), scheduled visits take precedence over unscheduled visits. Once this rule has been applied, the measurement closest to the target day will be used. If there are two observations which have the same difference in days to the planned day (but are not on the same day), the later of the two values will be selected.

Derivation of last, minimum and maximum values where relevant in safety analyses will consider all available values, regardless of whether they were selected in the visit window.

The derivation of the maximum value of an ECG interval (or worst case of the morphological assessment, if applicable) will consider all on-treatment values (whether or not selected in any time window; see [Section 6.1.6](#) for definition of on-treatment).

Two different situations are envisaged, which are described in the following tables:

- Visit windows for variables scheduled to be assessed at all or many visits
- Visit windows for variables with a sparse visit schedule.

Table 6.7: 1 Visit windows for variables scheduled to be assessed at all or many visits

Period	Time Point	Target Day	Visit Window
Dose escalation	Week 2	15	2-21
	Week 4	29	22-35
	Week 6	43	36-49
	Week 8	57	50-63
	Week 10	71	64-77
	Week 12	85	78-91
	Week 14	99	92-105
	Week 16	113	106-119
	Week 18	127	120-133
Maintenance	Week 20	141	134-154
	Week 24	169	155-182
	Week 28	197	183-210
	Week 32	225	211-238
	Week 36	253	239-266
	Week 40	281	267-301
	Week 46	323	≥ 302

The relevant variables are expected to include body weight measured at the clinic and BMI derived from this, vital signs, routine non-fasting laboratory safety variables, 12-lead ECG and the mental health questionnaires (C-SSRS, PHQ-9).

These visits windows will also be used for waist circumference, although this is not scheduled to be captured at all weeks displayed.

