7.4.1 Primary analysis of the primary endpoint(s)

The primary analysis of the primary endpoint will be performed on the FAS, using planned maintenance treatment, and including all data censored for COVID-19 related early treatment discontinuation. This specifies a hypothetical estimand strategy for the intercurrent event of pandemic-related early treatment discontinuation, and a treatment policy strategy for the intercurrent event of non-pandemic-related early treatment discontinuation.

A COVID-19 related early treatment discontinuation is defined as either of the following situations):

- Direct patient COVID-19 infection: Reason for early treatment discontinuation is given on the End of Treatment eCRF page as “Adverse Event” and a treatment-emergent AE of “COVID-19” is recorded.
- Other COVID-19 restriction (site access, drug supply, quarantine, etc) which meant that study treatment could not be continued: Reason for early treatment discontinuation is given on the End of Treatment eCRF page as “Other” and the supporting comments indicate clearly “COVID-19”.

Further, “censored for” COVID-19 related treatment discontinuation is clarified to mean in practice that for patients who had a COVID-19 related treatment discontinuation (and only for these patients), only the on-treatment data will be used, as defined in [Section 6.1.6](#).

Missing data will be modelled based on what was observed up to the occurrence of these intercurrent events using direct likelihood approaches, which is a valid approach under the assumption that data are MAR.

An MMRM will be fitted to the percentage change in body weight values at each scheduled week (calculated as per [Section 6.7](#)) for this purpose. The MMRM will include fixed effects for baseline body weight as a continuous linear covariate, and treatment, gender, visit, treatment by visit interaction and baseline by visit interaction as factors. The Kenward-Roger approximation will be used to estimate the denominator degrees of freedom.

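### Absolute weight change (kg) is modelled on on-treatment data only, while percentage change and responders from the same weights are not, and no visible reason covers the difference

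*SAP*

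**What the plan says.** SAP 7.5.2 sets one data rule for all continuous secondary endpoints: "The analysis of continuous secondary endpoints will be performed on the FAS, using planned maintenance treatment, and including only on-treatment data". It applies whether or not the discontinuation was related to COVID-19. The same subsection lists the endpoints concerned: "absolute changes from baseline in body weight, waist circumference, systolic BP and diastolic BP". Each is then fitted with an MMRM that gives adjusted differences from placebo with 95% confidence intervals.

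The other weight endpoints follow a different rule. The primary analysis of percentage change (SAP 7.4.1) is done "including all data censored for COVID-19 related early treatment discontinuation". The SAP describes this as a treatment policy strategy for discontinuations not related to the pandemic and a hypothetical strategy for those that are. For the 5, 10 and 15% thresholds, SAP 7.5.2 says: "The analysis of responder secondary endpoints (which are defined only at Week 46) will be aligned with the estimand strategy specified in" Section 7.4.1.

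SAP 5.2.2 ties all of these to one source: "All secondary endpoints defined using body weight will use clinic visit measurements of body weight, similarly to the primary endpoint".

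The only visible explanation near the on-treatment rule is a remark that off-treatment capture "which relates to endpoints other than those derived from body weight is not expected in any structured way".

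Two further rules fix what on-treatment means in practice. SAP 6.1.6 extends the safety definition (first dose to 28 days after last dose) to efficacy: "Efficacy data will also use the same 28 day definition of" on-treatment. SAP 6.7 sets the order of operations: "Prior to applying the visit windows specified below, it will first be determined whether the data record is on-treatment". Protocol 6.2.3 asks patients who stop drug early to come back for a weight every 4 weeks until Week 46.

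**The concern.** Kilogram change and percentage change are the same measurement on two scales. Where they are modelled with the same terms, a reader will take them as one result in two units. Here they target different estimands. The kg difference estimates the effect as if nobody had stopped drug. The percentage difference and the responder odds ratios include what happened after stopping, except for COVID-19 related stops.

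The SAP's remark on unstructured capture is a sound reason for waist circumference and blood pressure. By its own wording it leaves out endpoints derived from body weight, and off-treatment weights are exactly what the protocol plans to collect.

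If drug effect is lost after stopping, the modelled kg difference is expected to look more favourable than a kg difference on the primary data rule, with nothing in the visible text telling the reader why. If the effect is kept, no such gap is expected.

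**Working it through.** **1. The rules side by side**

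| Endpoint | Weights used | Off-treatment weights after a non-COVID-19 stop | After a COVID-19 related stop |
|---|---|---|---|
| Percentage change (SAP 7.4.1) | clinic, eCRF | used | dropped |
| 5/10/15% responders (SAP 7.5.2) | same | used | dropped |
| Change in kg (SAP 7.5.2) | same | **dropped** | dropped |

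The kg model keeps the terms of the primary model, because baseline body weight is already the relevant baseline. Apart from the response scale, the data rule is the only difference. It affects patients who stop for reasons other than COVID-19 and are weighed more than 28 days after the last dose.

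**2. Who loses the Week 46 kg value**

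Inputs: weekly dosing from day 1; last planned injection on day 316 (protocol Flow Chart footnotes); on-treatment to last dose + 28 days (SAP 6.1.6); Week 46 window from day 302, target day 323 (SAP Table 6.7: 1).

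- Dose days are 1 + 7k for k = 0 to 45, so there are 46 doses, the last on day 316. Stopping early means the last dose is one of doses 1 to 45.
- To reach the window, last dose + 28 ≥ 302, so the last dose must be on day 274 or later. Day 274 = 1 + 7 × 39 is dose 40. Doses 1 to 39 (last on day 267) fail: 39/45 = 87%.
- To be on-treatment on target day 323, the last dose must be on day 295 or later. Day 295 = 1 + 7 × 42 is dose 43. Doses 1 to 42 (last on day 288) fail: 42/45 = 93%.

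These are shares of possible stopping times, not of patients. The patients concerned still contribute earlier on-treatment weights to the MMRM.

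**3. Planning inputs used for scale**

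The plan gives no figure for this mismatch. The inputs borrowed below (10-point effect, SD 7, 70 per group, zero placebo effect; protocol 7.5) were checked against the linear column of protocol Table 7.5: 1. The check was a simulation of the three success criteria with only the linear model fitted and an assumed critical value of 2.3. For true maximum effects of -9.0, -9.5, -10.0, -10.5 and -11.0 it gave 48.9, 68.8, 83.9, 93.3 and 97.8%, against the stated 48.9, 67.8, 82.8, 92.4 and 97.1%.

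Planning standard error of a dose-placebo difference: 7 × √(2/70) = 1.18 points.

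**4. Illustrative size of the gap**

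The documents give no discontinuation or regain rates. Assumed: d = 10-30% of patients on active drug discontinue and are weighed off-treatment at Week 46; f = 50-100% of the effect is lost; body weight 100 kg, so that 1 point = 1 kg.

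- Gap = d × f × 10: from 0.1 × 0.5 × 10 = 0.5 to 0.3 × 1.0 × 10 = 3.0 kg.
- Against the planning SE: 0.5/1.18 = 0.4 to 3.0/1.18 = 2.5.
- With an assumed placebo shift s of ±2 kg among discontinuers, gap = d × (10f − s): from 0.1 × (5 − 2) = 0.3 to 0.3 × (10 + 2) = 3.6 kg.
- With f = 0 and s = 0, the gap is 0.

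The formula takes the planned 10 points as the on-treatment effect. If 10 points is instead the treatment policy effect, the on-treatment effect is 10/(1 − df) and the gap is 10df/(1 − df): from 0.5/0.95 = 0.5 to 3/0.7 = 4.3 kg.

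**The case against.** The on-treatment rule is stated openly, and the protocol permits it. Protocol 7.2.1 foresees on-treatment efficacy analyses, and protocol 7.3 leaves missing-data handling for the other secondary endpoints to the SAP. A secondary endpoint may target its own estimand. This stands, and no departure from the protocol is claimed.

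The rule also has some logic. The 28-day limit matches the period in which the listed anti-obesity drugs other than GLP-1 agonists are barred after the last dose (protocol 4.2.2.1), so later weights may reflect other treatment. Off-treatment Week 46 records may include weights taken at home (protocol 6.2.3). Both points apply equally to the percentage and responder endpoints, where such data are accepted, and SAP 5.1 says home values entered on the eCRF will not be removed. Neither explains treating kg differently.

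SAP 6.6 describes a hypothetical strategy for the primary endpoint that drops off-treatment weights, so on-treatment kg may have a percentage counterpart. That supports keeping the on-treatment kg analysis, but not making it the only modelled one.

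SAP 7.4 plans descriptive summaries of body weight on all data, on all data censored for COVID-19 related stops, and on on-treatment data. This is real mitigation, but no visible analysis gives a model-based kg difference from placebo on the primary rule.

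Text is blacked out next to this subsection, and SAP 7.4.2 is not in the public copy, so a reason or a supplementary kg model may exist there. The point is therefore limited to what can be read.

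Finally, the size rests on assumptions. It presumes that discontinuers would otherwise have had the average effect, whereas the MMRM conditions on their own earlier weights. This stands: the kg range is an illustration only.

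**Conclusion.** The concern holds as a point of consistency within the SAP. Of the weight endpoints, only kg change is modelled under an on-treatment rule. The one visible reason does not reach it, although weights after stopping are planned up to Week 46.

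The firm result is structural: 39 of 45 early stopping points leave no eligible Week 46 kg value, or 42 of 45 if the weight is taken on the target day. The size of the gap between the two kg estimates cannot be derived from the documents. The 0.5-3.0 kg range rests on assumed discontinuation, loss of effect and body weight, with no placebo shift, and it widens under the other assumptions shown.

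The consequence is limited. The proof-of-concept test, MCPMod, target dose and sample size do not depend on this endpoint, and the trial has no key secondary endpoints. What is at stake is whether the reported kg effect can be read alongside the percentage and responder results.

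**What to change.** In SAP 7.5.2, take absolute change in body weight (kg) out of the on-treatment-only rule and analyse it with the Section 7.4.1 data rule: all data, censored only for COVID-19 related discontinuation. Keep the on-treatment kg MMRM as a supportive analysis, labelled as such. Leave waist circumference and blood pressure on-treatment only, where the SAP's remark applies.

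The cost is one sentence in the SAP, one data flag and one extra MMRM run on weights already collected, best settled before unblinding. The kg estimate may come out slightly less favourable. If the sponsor prefers to keep the present rule, the minimum is to state the reason and label the kg result as an on-treatment estimand wherever it appears beside the percentage result.
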